	
his/her supplementation must be completed before 1h before bedtime.
 
2. Biological sample collection:
 
The remaining post-test serum samples need to be collected for metabolomics analysis from patients on day 1 of admission, postoperative day 6, postoperative 1 month, postoperative 3 months, and postoperative 6 months.
 
3. Clinical data collection:
 
1) General information: gender, age, height, weight, BMI, ICG 15min retention time, name of surgery, duration of surgery, blood loss, blood transfusion, tumor stage, NRS2002, GLIM malnutrition assessment (diagnostic) criteria diagnosis.
 
2) Nutritional indicators: Nutritional indicators such as serum albumin (ALB), prealbumin (PA), transferrin (TRF), and total serum protein (TP) were collected from patients on the 1st day of admission, the 6th postoperative day, 1 month postoperatively, 3 months postoperatively, and 6 months postoperatively.
 
(3) Liver function indexes: Liver function indexes such as alanine aminotransferase(ALT), alanine transaminase(AST), γ-glutamyltransferase (GGT), cholinesterase (CHE), and total bilirubin (TBIL) were collected on the 1st day of admission, the 6th postoperative day, 1 month postoperatively, 3 months postoperatively, and 6 months postoperatively.
 
(4) Clinical outcome: collect the patients' postoperative clinical outcome indicators, such as: postoperative complication rate, recurrence-free survival, and quality of survival.
 
(5) Medical costs: collect the total cost of the patients' hospitalization, the cost of anti-infective drugs, and the cost of albumin during hospitalization.

Evaluation of the	
Indicators of effectiveness evaluation
 
Main efficacy indicators: serum albumin (ALB)
 
Secondary efficacy indicators: serum prealbumin (PA), alanine

efficacy of treatment	aminotransferase (ALT), azelaic transaminase (AST), cholinesterase (CHE), total bilirubin (TBIL), total hospitalization costs, relapse-free survival, and quality of life
	
Safety evaluation indicators
 
Incidence of gastrointestinal symptoms such as abdominal distension, diarrhea, nausea and vomiting, incidence of postoperative complications, and length of postoperative hospitalization

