3.1 Types of Research Designs

Types of study designs: single-center, prospective cohort studies

Research Center: Drum Tower Hospital, Medical School of Nanjing University

Grouping method: non-randomized, open, enrolled according to patients' wishes

[figure not shown]
Sample size calculation basis and formula:

This study was a single-center prospective cohort study with two groups, the test group and the control group, and the serum albumin level of the study subjects was the primary endpoint outcome indicator observed. Based on the review of previous literature^[28] and reference to the results of the pretest, it was expected that the albumin level before LES intervention was 34.2 ± 3.9 g/L and the albumin level

after LES intervention was 37.5 ± 5.4 g/L, with a two-sided $\alpha=0.05$ and a degree of certainty of $1-\beta=90\%$. Using PASS15 software can be calculated to obtain $n=88$ cases. Based on the 1:1 grouping, 44 subjects were needed in each of the test and control groups, and assuming a 20% subject dropout rate, the final minimum number of subjects needed was 53 in each of the test and control groups, for a total of at least 106 subjects included.

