5.1 Research Methodology

1) Nutritional Assessment

All patients were screened for nutritional risk using the NRS 2002 scale within 24 h of admission, and a score of ≥ 3 was considered to be at nutritional risk; patients at nutritional risk were assessed for nutrition using the PG-SGA scale and diagnosed with malnutrition according to the GLIM Malnutrition Assessment (Diagnosis) Criteria.

2) Nutritional support therapy

The target intake for all patients was 25-30 kcal/kg/d. Nutritional supportive therapy was given to patients who were at nutritional risk and could not achieve the target intake. Oral nutritional supplements were preferred, and enteral nutritional supplementation was used in patients who still could not achieve 60% of the target amount. Supplemental parenteral nutrition was considered if patients could not achieve 60% of the target amount for 7 days after admission to the hospital.

3) Interventions

From the total daily intake, patients in the test group were divided into approximately 250kcal for late-evening snacks 1h before bedtime (200-275kcal total, 11.5g-18g protein, 25-55g complex carbohydrates); patients in the control group did not eat any more food 1h before bedtime.

Preparations used:

- ① Enteral nutrition powder: 450kcal/15.9g/100g;
- ② Whole protein type enteral nutrition suspension, energy density 1kcal/ml, protein 0.05g/ml, complex carbohydrate 0.126g/ml;
- ③ Whey protein powder, protein content >80g/100g.

[figure not shown]
4) Biological sample collection

Post-test residual serum samples from patients on day 1 of admission, day 6 postoperatively, 1 month postoperatively, 3 months postoperatively, and 6 months postoperatively were collected for metabolomic analysis to see if the metabolic pattern of the patients was altered in LES mode.

5) Clinical outcomes

The postoperative complication rate, tumor recurrence rate, recurrence-free survival, postoperative hospitalization time, total hospitalization cost, and cost of anti-infective drugs of the subjects after admission to the hospital were counted, and the chi-square test and independent samples t-test were performed to compare the differences, in order to find out whether the clinical outcomes had been improved under the LES model.

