A data safety monitoring program will be established for clinical studies according to the level of risk. All adverse events will be recorded in detail, appropriately handled and followed up until properly resolved or stabilized, and serious adverse events and unintended events, etc., will be reported to the Ethics Committee, the competent authority, the sponsor, and the drug regulatory authority in a timely manner according to the regulations; the principal investigator will conduct a cumulative review of all adverse events on a regular basis, and convene a meeting of the investigators to assess the risks and benefits of the study, if necessary; the injuries or discomfort is no more likely and no greater in magnitude than that encountered in daily life or than that of a routine examination, and that data and safety monitoring can be accomplished by the principal investigator.

10. Statistical processing

应用 SPSS26.0 统计软件对临床数据进行描述性统计，符合正态分布的计量资料以均数±标

准差($\bar{x} \pm s$)表示, 组间采用 t 检验, 不符合正态分布的计量资料以中位数(四分位间距) [M(IQR)] 表示, 组间采用 Mann-Whitney U 检验。计数资料用百分比[n(%)]表示, 组间比较采用卡方检验, $P<0.05$ 为有显著性统计学意义。采用 STATA12.0 中的 Kaplan-Meier 法计算各组复发率及无复发生存期, log-rank 检验进行组间比较。SPSS26.0 statistical software was applied to carry out descriptive statistics of the clinical data, and the measurements that conformed to normal distribution were expressed as mean \pm standard deviation ($\bar{x} \pm s$), and t-test was used between the groups, and the measurements that did not conform to normal distribution were expressed as median (inter-quartile spacing) [M(IQR)], and Mann-Whitney U-test was used between the groups. Count data were expressed as percentages [n(%)], and the chi-square test was used for between-group comparisons, with $P<0.05$ considered statistically significant. The Kaplan-Meier method in STATA 12.0 was used to calculate the recurrence rate and recurrence-free survival in each group, and the log-rank test was used for between-group comparisons.

11. Ethical principles of clinical research

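### The safety indicators have no statistical rule beyond a difference test at P<0.05, so for events with a control rate of about 15% or lower a true doubling would be non-significant more often than not

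*Combined protocol and SAP*

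**What the plan says.** The synopsis, under safety evaluation indicators, names "Incidence of gastrointestinal symptoms such as abdominal distension, diarrhea, nausea and vomiting, incidence of postoperative complications, and length of postoperative hospitalization". The first two are binary for each patient; the third is continuous.

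The statistical methods appear in the synopsis, in section 3.2 (data analysis) and in section 10, with the same content. Counts are shown as n (%) and compared by chi-square: "the chi-square test was used for between-group comparisons, with $P<0.05$ considered statistically significant". Continuous measures are compared by t-test, or by Mann-Whitney if not normal. Section 5.1, item 5, covers complications and postoperative stay among the clinical outcomes and says "the chi-square test and independent samples t-test were performed to compare the differences". None of these places plans a risk difference, ratio, confidence interval, margin or upper bound.

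Section 3.1 bases the sample size on serum albumin only: 44 per group, raised to 53 for 20% dropout.

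Sections 8 and 9 provide for adverse event recording, CTCAE grading, a causality table and a regular cumulative review by the principal investigator, with a risk-benefit meeting if needed. They set no numerical criterion.

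**The concern.** A difference test has two outcomes: a difference is shown, or it is not. The second says little unless the study could have shown a difference worth knowing about. This study was not sized for any safety event, and the plan offers no quantity that would tell a reader how large an increase remains compatible with the data.

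Tolerance is a real question here. Section 8 gives bloating and diarrhea as its example adverse events, and section 3.2 allows the snack from the second postoperative day. The symptoms in the synopsis, and the infections, bile leakage and liver failure defined in section 7.2, can each be tabulated separately, and some may be uncommon. For an uncommon event, a bare non-significant P value could be taken as reassurance that the data cannot give.

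**Working it through.** **1. The plan's own sample size.** From section 3.1: means 34.2 and 37.5 g/L, SDs 3.9 and 5.4, two-sided 5%, power 90%.

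- Difference 37.5 − 34.2 = 3.3; pooled SD = √((3.9² + 5.4²)/2) = 4.71.
- Normal formula: n = 2(1.960 + 1.282)² × 4.71²/3.3² = 42.8, so 43 per group. The noncentral t version gives 44 (power 0.901), as stated.
- 44 × 1.2 = 52.8, so 53 per group, as stated.

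The figures reproduce. No safety event enters them.

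**2. Chance of missing a true doubling of a binary event.** Control rates are assumptions, because the documents give none. Method: with n per group, list all pairs of counts (a, b), weight each pair by Bin(a; n, p) × Bin(b; n, 2p), and add up the weights of pairs whose Pearson chi-square exceeds 3.841. One minus that sum is the miss rate.

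| Control vs test rate | Missed, 53 per group | Missed, 44 per group |
|---|---|---|
| 5% vs 10% | 85% | 84% |
| 10% vs 20% | 70% | 73% |
| 15% vs 30% | 53% | 59% |
| 20% vs 40% | 37% | 45% |
| 25% vs 50% | 22% | 30% |
| 30% vs 60% | 12% | 19% |

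The exact 50% point lies at a control rate of about 16% (53 per group) or 18% (44 per group). With Yates' correction it moves to about 19% or 21.5%, and the 10% vs 20% row becomes 79% or 84%.

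**3. What an interval would show.** Take 10/53 against 5/53 patients with a symptom.

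- Pearson chi-square = 106 × (10 × 48 − 5 × 43)²/(53 × 53 × 15 × 91) = 1.94, P = 0.16.
- Difference: 0.189 − 0.094 = 0.094. Wilson 95% limits are 0.106 to 0.314 and 0.041 to 0.203.
- Newcombe lower limit: 0.094 − √((0.189 − 0.106)² + (0.203 − 0.094)²) = −0.042.
- Newcombe upper limit: 0.094 + √((0.314 − 0.189)² + (0.094 − 0.041)²) = 0.230.

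The P value reads as not significant; the interval runs from 4 points lower to 23 points higher. With equal counts of 5/53 in each group, the interval is still ±12 points; with 4/44 in each, ±13 points.

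**4. Postoperative stay.** Assume a coefficient of variation of 0.3 to 1.0. Power to detect a doubled stay is then 84% to over 99% on the raw scale and 97% to over 99% on the log scale. A smaller shift of 0.5 SD is detected 72% (53 per group) or 64% (44 per group) of the time.

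**The case against.** The strongest reply is that the plan nowhere says non-significance means safety. That is correct. A reader might infer such a claim from section 9, which says "the injuries or discomfort is no more likely and no greater in magnitude than that encountered in daily life". In context that clause explains why monitoring can be left to the principal investigator. It is a minimal-risk statement about oversight, and the test hypothesis in section 2.3 makes no safety or equivalence claim. Section 5.1 also asks whether clinical outcomes improved, and a two-sided difference test suits that question for complications and stay.

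A reader might also infer that a doubling of any harm would usually be missed. The table contradicts this for control rates of 20% or more, and step 4 contradicts it for stay.

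It would also be wrong to say that safety has no decision process, since sections 8 and 9 provide qualitative review. Nor does the snack add to the planned daily intake: sections 3.2 and 5.1 take its calories out of the day's total, so what changes is timing.

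Finally, intervals can be computed later from the n (%) tables, and their absence affects every endpoint. Both are true. But nothing commits the report to them, and qualitative case review does not estimate a between-group difference.

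**Conclusion.** The point holds in a limited form. The only statistical rule for the safety indicators is a difference test at P<0.05, with no estimate, interval or bound, in a study sized for albumin. If a single symptom or complication has a control rate of about 15% or lower, a true doubling gives P>0.05 more often than not with 44 to 53 per group: 53% to 85% of the time across control rates of 5% to 15%. At 20% or more it is more often detected. The statement rests on assumed control rates, on the uncorrected Pearson test and on 44 to 53 analysed per group. It does not cover postoperative stay.

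An interval would improve the report but would not settle safety. A reader might want to call its upper limit the largest increase the trial cannot exclude. The design does not support that: patients choose their group (section 3.1), and section 4.4, items 5 and 6, removes patients who depart from their regimen, which could take out those who could not tolerate the snack. The limit describes sampling error only.

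This should be changed. It affects how the safety results are read, not the albumin analysis.

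**What to change.** In section 10, and to match in the synopsis, section 3.2 (data analysis) and section 5.1, item 5:

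- For each gastrointestinal symptom and each complication, report the risk difference (test minus control) with a two-sided 95% Newcombe interval.
- For postoperative stay, report the mean difference or, if the data are not normal, the Hodges-Lehmann median difference, with a 95% interval.
- Keep the P values for these indicators as descriptive.
- State that P>0.05 will not be read as evidence of safety or equal tolerability.
- Quote the upper confidence limit with the note that it reflects sampling error only, because groups are self-selected and section 4.4 removes non-adherent patients.
- Count safety events in all enrolled patients who started the regimen of their group, including those later removed under section 4.4.

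The cost is a few sentences of analysis text, an extra column in the safety tables, and keeping the safety records of removed patients in the count. No extra patients are needed. The downside is a more cautious safety statement, because the intervals will be wide.

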42. Have you worried about getting enough nourishment?	1	2	3	4
43. Have you felt full up too quickly after beginning to eat?	1	2	3	4
44. Have you worried about your weight being too low?	1	2	3	4
45. Have you been less active than you would like to be?	1	2	3	4
46. Have you found it difficult to finish things?	1	2	3	4
47. Have you needed to sleep during the day?	1	2	3	4

During the past four weeks:

48. Has the disease or treatment had any effect on your sex life?	1	2	3	4
---	---	---	---	---
